3.4 STUDY CALENDAR

On study assessments can be performed within ± 7 days of the specified time, unless otherwise indicated. Treatments may be delayed up to 7 days to accommodate scheduling.

Procedure	Screening	Baseline ²	Cycles = 28 days ¹										End of Treatment/ Disease Progression ¹³	Post Therapy Follow-up ⁴
			Day 1	2	3	4	5	7	15 ²⁸	21	28	Cycle 2 ²² Day 1		
History	X											X	X	
Physical exam ³	X	X							X				X	
PTT/PT ²³	X	X												
Viral Markers Protocol Screen ¹⁷	X													
CBC diff ^{5, 20}	X	X						X ¹⁴	X	X		X	X	
Acute Care Panel ^{6,20}	X	X						X ¹⁴	X	X		X	X	
Hepatic Panel ^{7, 20}	X	X						X ¹⁴	X	X		X	X	
Mineral Panel (mCRPC only) ²⁴			X						X					
LDH, Creatine kinase, Uric Acid, Total Protein (mCRPC only)		X										X		
Pregnancy test ⁸	X	X										X		
CT scan ¹²	X ¹⁵	X											X	
CT c/a/p and bone scan (mCRPC only)	X	X										X ²⁵	X	
PSA (mCRPC only)		X										X ²⁵	X	
Clinical disease assessment		X										X	X	
ECG	X	X	X ²⁷						X ²⁷			X ²⁷		
Echocardiogram ²¹	X													
Whole blood, plasma, hair ²⁶ and saliva for correlative studies ^{9, 29}			Refer to tables in section 5. Table 11 – Phase 1 and Phase 2 SCLC; Table 13 – UC expansion; Table 14 – mCRPC expansion											

Procedure	Screening	Baseline ²	Cycles = 28 days ¹										End of Treatment/ Disease Progression ¹³	Post Therapy Follow-up ⁴
			Day 1	2	3	4	5	7	15 ²⁸	21	28	Cycle 2 ²² Day 1		
PK ^{16,29}			X	X	X				X ¹⁹					
Biopsies ¹⁰		X				X							X	
EP0057			X						X			X		
Olaparib ¹¹					X	X	X	X		X				
Follow-up phone call														X

¹ Number of cycles depends on disease progression and development of intolerable side effects

² Baseline procedures are performed within 2 weeks of initiation of study therapy with the exception of pregnancy test which must be performed within 3 days prior to the initiation of study therapy. If the procedure was performed during the appropriate timeframe at screening, it is not necessary to repeat at baseline.

³ Symptom-directed physical examinations will be performed as clinically indicated in the investigator's judgment

⁴ Follow-up for survival will be carried out every 3 months

⁵ Includes Neutrophils, Lymphs, Monos, Eos, Basos, WBC, RBC, Hemoglobin, Hematocrit, RBC Indices, MCV, RDW, Platelet. Results should be available prior to administration of study drugs

⁶ Includes Sodium (NA), Potassium (K), Chloride (CL), Total CO₂ (Bicarbonate), Creatinine, random Glucose, Urea or blood urea nitrogen [BUN], eGFR.

⁷ Includes Alkaline Phosphatase, ALT/GPT, AST/GOT, Total Bilirubin, Direct Bilirubin

⁸ Only for IOCBP; may be obtained up to 3 days prior to Day 1 of each cycle.

⁹ Blood, plasma, hair and saliva samples will be collected at multiple time points during cycles 1,2 and each cycle thereafter for hair collection (for specific timepoints on correlative samples collection please refer to section 5.1.1 for Phase I and Phase II cohorts, section 5.1.2 for UC expansion cohort and section 5.1.3 for mCRPC expansion cohort). C1D15 timepoint for correlative studies will only be done for Phase II SCLC cohort. Only whole blood will be drawn for that cohort at that timepoint.

¹⁰ Optional biopsies will be obtained at baseline, during the first treatment cycle (approximately 24 hours after the first dose of olaparib) and at disease progression. In the mCRPC cohort, biopsy at baseline is mandatory.

¹¹ PO days 3-13 and days 17-26, as indicated in Section 3.2. There should be at least a 48-hour window between EP0057 and olaparib except dose level 5B which allows the interval to be abbreviated to 24 hours. Olaparib can be taken continuously if EP0057 is missed for any reason.

¹² Performed after every 2 cycles

¹³ Approximately 4 weeks after treatment discontinuation

¹⁴ Only done in cycle 1

¹⁵ Only done in phase 2

¹⁶ Phase 1 portion of the study in cycles 1 and 6 only.

¹⁷ Within 3 months of C1D1.

¹⁹ D15 PKs can be obtained +/- 5 days.

²⁰ Weekly during C1, at every visit for subsequent cycles, and whenever clinically indicated

²¹ Within 4 weeks

²² C2 and all subsequent cycles, Day 1

²³ All patients should get tested at screening. Patients taking warfarin will be monitored at least weekly for C1, then monthly if the INR is stable.

²⁴ Includes Albumin, Calcium, Magnesium and Phosphorus

²⁵ PSA is to be analyzed along with measurable lesions evaluated by CT scan of chest/abdomen/pelvis and technetium 99 bone scan every 3 cycles (every 12 weeks).

²⁶ Hair collection will only be done for Phase I cohorts.

²⁷ ECG required within 60 -180 minutes post-infusion for first two cycles of EP0057 for patients with any conduction abnormality on baseline ECG.

²⁸ Day 15 assessments not required for patients on olaparib only.

²⁹ This protocol targets patients with aggressive tumors and, historically, minimal tissue is available (majority of patients are unresectable at diagnosis). Hence, the priority is to perform biopsies followed by treatment initiation as quickly as possible. In instances where research labs including PKs cannot be obtained due to scheduling conflicts, samples may be omitted or collected in a delayed fashion.

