3.2.2 Olaparib

Olaparib tablet at the appropriate dose level will be given orally on days 3-13* and days 17-26* twice daily (*there should be at least a 48-hour window between olaparib and EP0057 except dose level 5B which allows the window to be abbreviated to 24 hours). The correct number of 25 mg, 100 mg, 150 mg or 200 mg tablets comprising the appropriate dose should be taken at the same times each day with approximately 240 mL of water. A light snack (biscuits/ toast) is advised at the time of dosing to help alleviate nausea but no specific timing needs to be observed. The olaparib tablets should be swallowed whole and not chewed, crushed, dissolved or divided.

Olaparib will be dispensed at the start of each cycle. Patients will be provided with a pill diary ([Appendix C](#), Section 16.3), instructed in its use, and asked to bring it with them to each appointment.

For Phase II, it is recommended, but not required, that growth factors be given prophylactically starting cycle 1 on the phase II part of the study. Please note that G-CSF should not be used within at least 24 hours of the last dose of EP0057 administration.

If vomiting occurs shortly after the olaparib capsules are swallowed, the dose should only be replaced if all of the intact capsules can be seen and counted. Should any patient enrolled on the study miss a scheduled dose, the patient will be allowed to take the scheduled dose up to a maximum of 2 hours after that scheduled dose time. If greater than 2 hours after the scheduled dose time, the missed dose should not be taken, and the patient should take their allotted dose at the next scheduled time.

Olaparib can be taken continuously in cases where EP0057 is missed for any reason.

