3.3.2 Dosing Delays/Dose Modifications and Management of Toxicities

- In the case of toxicity, appropriate medical treatment should be used (including anti-emetics, anti-diarrheals, etc.).
- Once a patient has a dose reduction for toxicity, the dose will not be increased.
- A maximum of 2 dose reductions is permitted
- If either agent is discontinued due to toxicity, the patient may continue on the other agent.
- Participants continuing to experience toxicity at the off treatment visit will be contacted for additional assessments until the toxicity has resolved or is deemed irreversible. Patients must remain on the study to have additional assessment.
- For AEs that are unrelated to the study drugs, study drug may be held for up to 21 days at the discretion of the PI.
- The associate investigator and/or PI will determine whether one or both drugs are responsible for an observed toxicity and will manage that toxicity as described below.

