3.3.2.1 Hematologic toxicities

Table 8. Dose Modification and Management of Hematologic Adverse Events

Observation	Action
On day 1 and 15 Absolute neutrophil count (ANC) \geq 1500/mcL AND Platelets \geq 75,000/mcL AND Hemoglobin \geq 8 g/dL	No interruption.
On day 1 and 15 ANC $<$ 1500/mcL OR Platelets $<$ 75,000/mcL OR Hemoglobin $<$ 8 g/dL	If any weekly evaluation demonstrates grade \geq 3 neutropenia or grade \geq 2 thrombocytopenia, a repeat hematology assessment will be obtained 2-4 days later. On first occurrence , hold the drug(s) causing the toxicity for up to 21 days until ANC \geq 1500/mcL, platelets \geq 75,000/mcL, and hemoglobin \geq 9 g/dL. The associate investigator and/or PI will determine whether one or both drugs are responsible for an observed toxicity and will initiate appropriate medical therapy and no change in dose upon re-initiation. On second occurrence , hold the drug(s) causing the toxicity for up to 21 days until ANC \geq 1500/mcL, platelets \geq 75,000/mcL, and hemoglobin \geq 9 g/dL. Initiate appropriate medical therapy. Treatment with olaparib or EP0057 may be restarted at one dose level (DL) lower. Patients whose counts have not recovered to ANC \geq 1500/mcL, platelets \geq 75,000/mcL, and hemoglobin \geq 9 g/dL after 21 days should be removed from the drug causing the toxicity.
At any time during cycle Grade 4 hematologic AE	On first occurrence , hold the drug(s) causing the toxicity for up to 21 days until ANC \geq 1500/mcL, platelets \geq 75,000/mcL, and hemoglobin \geq 9 g/dL. Initiate appropriate medical therapy. Treatment with olaparib or EP0057 may be restarted at one DL lower. On second occurrence , discontinue the drug(s) causing the toxicity. Follow patient until

Table 8. Dose Modification and Management of Hematologic Adverse Events

Observation	Action
	resolution/stabilization of toxicity. Patients whose counts have not recovered to ANC \geq 1500/mcL, platelets \geq 75,000/mcL, and hemoglobin \geq 9 g/dL after 21 days should be removed from the drug causing the toxicity. See section 3.3.2.1 for exceptions.
Toxicities requiring more than 2 dose reductions	Remove patient from the drug causing the toxicity.

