- Treatment may be delayed for a maximum of 21 days after holding the treatment for toxicities that develop and do not resolve as defined above (the following AE's are exempt from hold: lymphopenia, or leukopenia in the absence of grade 3 or higher neutropenia).
- Weekly blood counts will be obtained during the first cycle, and then at day 1 and 15 of subsequent cycles.
- Management of prolonged hematological toxicities while on study treatment
 - If a patient develops prolonged hematological toxicity such as:
 - \geq 2 week interruption/delay in study treatment due to CTC grade 3 or worse anemia and/or development of blood transfusion dependence
 - \geq 3 week interruption/delay in study treatment due to CTC grade 3 or worse neutropenia (ANC $<$ 1,000/mcL)
 - \geq 3 week interruption/delay in study treatment due to CTC grade 3 or worse thrombocytopenia (Platelets $<$ 50,000/mcL)
 - Weekly differential blood counts including reticulocytes (calculate reticulocyte index (RI), RI = reticulocyte count x hematocrit (Hct)/normal Hct; a value of 45 is usually used for normal Hct) and peripheral blood smear should be performed. If any blood parameters remain clinically abnormal after 4 weeks of dose interruption, the patient should be referred to hematologist for further investigations. Bone marrow analysis and/or blood cytogenetic analysis should be considered at this stage according to standard hematological practice.
 - Development of a confirmed myelodysplastic syndrome or other clonal blood disorder should be reported as an SAE. Study treatment should be discontinued if diagnosis of myelodysplastic syndrome is confirmed.

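### Calendar footnote 28 waives the Day 15 blood count that section 3.3.2.1 requires, and does not exempt patients whose EP0057 was discontinued for hematologic toxicity

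*Combined protocol and SAP*

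**What the plan says.** Section 3.3.2.1 sets the schedule of counts: "Weekly blood counts will be obtained during the first cycle, and then at day 1 and 15 of subsequent cycles". It makes no exception for patients on one drug. The threshold row of Table 8 (ANC below 1500/mcL, platelets below 75,000/mcL or hemoglobin below 8 g/dL) is tied to Days 1 and 15 and holds whichever drug is judged responsible. The grade 4 row applies "At any time during cycle".

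Footnote 28, attached to the Day 15 column of the section 3.4 calendar, reads "Day 15 assessments not required for patients on olaparib only". The CBC row has a mark in that column.

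A patient can reach olaparib alone because of low counts. Table 8 removes only the drug judged causal, and section 3.3.2 says "If either agent is discontinued due to toxicity, the patient may continue on the other agent".

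Four other provisions bear on the gap:

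- Footnote 20, on the CBC row, reads "Weekly during C1, at every visit for subsequent cycles, and whenever clinically indicated". Section 3.3.6 says much the same.
- The calendar marks a CBC on Day 21.
- Section 3.3.2.1 orders weekly counts after an interruption of at least 2 weeks for grade 3 or worse anemia and/or transfusion dependence, or of at least 3 weeks for grade 3 or worse neutropenia or thrombocytopenia.
- After a second grade 4 event, Table 8 says "discontinue the drug(s) causing the toxicity. Follow patient until" resolution or stabilization.

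**The concern.** Staff who work from the calendar will skip a count that staff who work from section 3.3.2.1 will take. Without it, the Day 15 half of the Table 8 threshold rule cannot be applied to olaparib.

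The patients who matter most are those who came off EP0057 because of their counts. They are foreseeable: all three dose-limiting toxicities described in section 1.2.16 involved neutropenia, one of them among the six patients at the recommended phase 2 dose. Section 14.2.3 names bone marrow as olaparib's target organ of toxicity. If low counts were attributed to EP0057 alone and olaparib contributed, a mid-cycle count is one of the checks that would show it. A fall that crosses a Table 8 threshold without reaching grade 4 could be found later than section 3.3.2.1 intends.

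**Working it through.** The plan gives no figure to reproduce. The check compares the rules and then counts days.

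**Do the rules conflict?** For a patient on olaparib alone in cycle 2 or later, section 3.3.2.1 requires a Day 15 count and footnote 28 says it is not required. Footnote 20 and section 3.3.6 tie later counts to visits or to clinical indication. Once the Day 15 visit is waived, they do not restore a scheduled count on that day.

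**Who is left uncovered?** The routes to olaparib alone after hematologic toxicity compare as follows.

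| Reason EP0057 was stopped | Other provision | Clearly covered? |
|---|---|---|
| Not recovered after 21 days, grade 3 or worse | Weekly counts, section 3.3.2.1 | Yes |
| Second grade 4 event, not yet resolved | Table 8 follow-up | Largely; no interval is given |
| Not recovered after 21 days, grade 2 (for example ANC 1000-1499/mcL) | None scheduled | No |
| More than two dose reductions needed | None scheduled | No |
| Counts recovered before olaparib alone continued | None scheduled | No |

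The grade 2 row follows from two limits in section 3.3.2.1. Recovery requires ANC of at least 1500/mcL, while the neutropenia trigger for weekly counts is ANC below 1000/mcL. Values in between meet the removal rule but not the trigger. The first row assumes that a hold of EP0057 alone counts as an interruption of study treatment, which is the reading more favorable to the plan.

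**How long is the gap?** Taking the next cycle's Day 1 as Day 29, the longest nominal gap in a later cycle is:

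- Section 3.3.2.1 (Days 1 and 15): 15 − 1 = 14 days, then 29 − 15 = 14 days. Longest gap 14.
- Footnote 28, Day 21 CBC done: 21 − 1 = 20 days, then 29 − 21 = 8 days. Longest gap 20, and 20/14 = 1.4 times.
- Footnote 28, Day 21 CBC not done: 29 − 1 = 28 days. Longest gap 28, and 28/14 = 2.0 times.

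A fall already present on Day 15 would be found 21 − 15 = 6 days later in the second case and 29 − 15 = 14 days later in the third.

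**Is the Day 21 count part of later cycles?** On the CBC row only the Day 7 mark carries footnote 14, which limits it to cycle 1. The Day 21 mark does not. But section 3.3.2.1 names only Days 1 and 15 for later cycles, and footnote 20 makes later counts depend on visits. Both cases therefore stay open.

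**Window.** Section 3.4 allows ±7 days on assessments. Used in opposite directions at the two ends, this can add up to 7 + 7 = 14 days to any of these gaps or take up to 14 off, so the figures are nominal.

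**The case against.** The strongest reply is that footnote 28 is a deliberate, specific exception. Days 1 and 15 are the EP0057 infusion days, and footnote 5 asks for results before study drug is given. With no Day 15 infusion, much of the purpose of that count lapses. Section 14.2.8 describes monthly hematologic monitoring for olaparib. Not requiring a count does not forbid one, and clinically indicated counts remain.

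Much of this stands. The waiver is reasonable when EP0057 ended for a non-hematologic reason. It is not a complete answer, because section 3.3.2.1 does not state the exception, Table 8 still sets a Day 15 rule for either drug, and footnote 28 does not separate patients with marrow toxicity from the rest.

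Three stronger readings are tempting, and the documents do not support them:

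- A reader might infer that everyone taken off EP0057 for low counts loses mid-cycle monitoring. The weekly-count rule in section 3.3.2.1 is denser than Days 1 and 15 and covers prolonged severe cases, and Table 8 covers unresolved second grade 4 events.
- A reader might infer that the gap simply doubles to 28 days. The calendar's Day 21 mark may hold it at 20, and the window blurs both figures.
- A reader might add that the Appendix C pill diary, which prints no-olaparib days, contradicts section 3.2.2 ("Olaparib can be taken continuously in cases where EP0057 is missed for any reason") and footnote 11. Continuous dosing is optional, and a patient who follows the diary only takes less drug. The missing page is a forms matter and not part of this point.

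**Conclusion.** The concern holds as a minor inconsistency in safety monitoring. Two current rules give opposite instructions for the Day 15 CBC in patients on olaparib only, and the waiver does not exempt those whose EP0057 was discontinued for hematologic toxicity. Its practical reach is the three groups not clearly covered elsewhere: grade 2 non-recovery, more than two dose reductions, and counts recovered before continuing on olaparib alone. For them the nominal longest gap goes from 14 days to 20 or 28, depending on whether the Day 21 CBC is done in later cycles.

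The safety effect is modest, because grade 4 rules apply throughout the cycle and clinically indicated counts remain. The documents do not say how many patients are on olaparib only. The two-stage decision rules, error rates and sample size are unaffected. The conflict itself rests on the wording alone; the size rests on the nominal visit days.

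**What to change.** Extend footnote 28 so that its present wording continues: *except the CBC, which is kept on Day 15 for patients whose EP0057 was discontinued for hematologic toxicity, until two consecutive cycles show no count below the Table 8 thresholds*. State the same exception in section 3.3.2.1, so that both places waive the Day 15 count for other olaparib-only patients and keep it for these.

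The two-cycle end point is a suggested value; the investigators may prefer another. Some end point is needed so that one past event does not require Day 15 counts indefinitely.

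The cost is a phrase in each place and one mid-cycle CBC per cycle for these patients, a blood draw that section 3.3.2.1 already requires.

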3.5 COST AND COMPENSATION

3.5.1 Costs

NIH does not bill health insurance companies or participants for any research or related clinical care that participants receive at the NIH Clinical Center. If some tests and procedures are performed outside the NIH Clinical Center, participants may have to pay for these costs. Medicines that are not part of the study treatment will not be provided or paid for by the NIH Clinical Center.

3.5.2 Compensation

Participants will not be compensated on this study.

3.5.3 Reimbursement

The NCI will cover the costs of some expenses associated with protocol participation. Some of these costs may be paid directly by the NIH and some may be reimbursed to the participant/guardian as appropriate. The amount and form of these payments are determined by the NCI Travel and Lodging Reimbursement Policy.

3.6 CRITERIA FOR REMOVAL FROM PROTOCOL THERAPY AND OFF STUDY CRITERIA

Prior to removal from protocol, effort must be made to have all subjects complete a safety visit approximately 30 days following the last dose of study therapy.

3.6.1 Criteria for Removal from Protocol Therapy

- Progressive disease
- Participant requests to be withdrawn from active therapy
- Unacceptable Toxicity as defined in Sections [3.1.1](#) and [3.3](#)
- Toxicity related dose delay lasting longer than 21 days in which case patient will be removed from the drug causing the toxicity.
- Investigator discretion
- Requirement for any of the prohibited study drugs as described in [Appendix B](#), Section [16.2](#) (Strong and moderate Inhibitors and Inducers of CYP3A)
- The subject becomes pregnant
- Active pneumonitis

3.6.2 Off-Study Criteria

- Participant requests to be withdrawn from study
- Investigator decision to end study
- Death
- Permanent loss of capacity to consent
- Screen failure

4 CONCOMITANT MEDICATIONS/MEASURES

- No other chemotherapy, hormonal therapy (HRT is acceptable) or other novel agent is to be permitted during the course of the study for any patient (the patient can receive a stable dose of corticosteroids during the study as long as these were started at least 4 weeks prior to treatment, as per exclusion criteria above). For the mCRPC cohort, patients may receive hormonal therapy in the form of GnRH agonists/antagonists as per eligibility criteria above and corticosteroids are permissible.
- Live virus and bacterial vaccines should not be administered whilst the patient is receiving study medication and during the 30 day follow up period. An increased risk of infection by the administration of live virus and bacterial vaccines has been observed with conventional chemotherapy drugs and the effects with olaparib are unknown.
- No concomitant use of alternative, complementary therapies or over-the-counter agents will be allowed without approval of the PI. All medications must be recorded in the case report form and be reviewed by the treating physician at each visit.
- Caution should be exercised in the concomitant use of any medication that may markedly affect renal function. Such medications may be used with caution as deemed essential for treatment, or if already in use prior to entry in the study without any effect on renal function.
- Caution should be exercised in concomitant use of any medication that may significantly affect hepatic CYP450 drug metabolizing activity by way of enzyme induction (e.g. Phenytoin) or inhibition (e.g. ketoconazole, ritonavir, erythromycin) within 2 weeks before the first dose of olaparib and throughout the study period.
- Given this data, potent inhibitors or inducers of CYP3A4 (as outlined in [Appendix B](#), Section [16.2](#) must not be used during this study).
- CYP3A4 known potent inhibitors: wash-out period 1 week, or at least 4.5x elimination half-lives for drugs and metabolites known to inhibit CYP3A subfamily enzymes: Ketoconazole, itraconazole, ritonavir, indinavir, saquinavir, telithromycin, clarithromycin and nelfinavir
- CYP3A4 inducers (potential reduction in efficacy of olaparib) a wash-out period for 3 weeks for Phenytoin, rifampicin, rifapentine, rifabutin, carbamazepine, phenobarbital, nevirapine, modafinil and St John's Wort.
- Patients should avoid concomitant use of drugs, herbal supplements and/or ingestion of foods known to modulate CYP3A4 enzyme activity from the time they enter the screening period until 30 days after the last dose of study medication. *In vitro* data have shown that the principal enzyme responsible for the formation of the 3 main metabolites of olaparib is CYP3A4 and consequently, this restriction is required to ensure patient safety.
- Olaparib inhibits CYP3A4 *in vitro* and is predicted to be a mild CYP3A inhibitor *in vivo*. Therefore, caution should be exercised when sensitive CYP3A substrates or substrates with a narrow therapeutic margin (e.g. simvastatin, cisapride, cyclosporine, ergot alkaloids, fentanyl, pimozide, sirolimus, tacrolimus and quetiapine) are combined with olaparib.
- Substrates of UGT1A1 should also be given with caution in combination with olaparib (e.g. irinotecan, nintedanib, ezetimibe, raltegravir or buprenorphine).

- Induction of CYP1A2, 2B6 and 3A4 has been shown in vitro with CYP3A4 CYP2B6 being most likely to be induced to a clinically relevant extent. The potential for olaparib to induce CYP2C9, CYP2C19 and P-gp is unknown. It cannot be excluded that olaparib upon co administration may reduce the exposure to substrates of these metabolic enzymes and transport protein. The efficacy of hormonal contraceptives may be reduced if co administered with olaparib.
- In vitro olaparib has been shown to be an inhibitor of P-gp, OATP1B1, OCT1, OCT2, OAT3, MATE1 and MATE2K and is a weak inhibitor of BRCP. It cannot be excluded that olaparib may increase the exposure to substrates of P-gp (e.g. statins, digoxin, dabigatran, colchicine), OATP1B1 (e.g. bosentan, glibenclamide, repaglinide, statins, and valsartan), OCT1 (e.g. metformin), OCT2 (e.g. serum creatinine), OAT3, MATE1 and MATE2K. In particular, caution should be exercised if olaparib is administered in combination with any statin.

